**LIST OF ABBREVIATIONS AND RELEVANT DEFINITIONS**

AE	Adverse Event
ABPA	Allergic Bronchopulmonary Aspergillosis
BAT trial	Bronchiectasis and long term Azithromycin Treatment trial
CRF	Case Record Form
CF	Cystic Fibrosis
CFU	Colony Forming Units
DSMB	Data Safety Monitoring Board
EudraCT	European drug regulatory affairs Clinical Trials
FEV1	Forced Expiratory Volume in 1 second
FVC	Forced Vital Capacity
GCP	Good Clinical Practice
GFR	Glomerular Filtration Rate
GP	General Practitioner
HRCT	High Resolution Computed Tomography
IB	Investigator's Brochure
ICF	Informed Consent Form
IMP	Investigational Medicinal Product
IMPD	Investigational Medicinal Product Dossier
LTRI-VAS	Lower Respiratory Tract Infection Visual Analogue Scale
METC	Medical research ethics committee (MREC); in Dutch: Medisch Ethische Toetsing Commissie (METC)
MIC	Minimum Inhibitory Concentration
Non-CF bronchiectasis	Non-Cystic Fibrosis bronchiectasis
Non-PDPE	non- protocol-defined pulmonary exacerbation
PDPE	protocol-defined pulmonary exacerbation
QoL	Quality of Life
QoL-B	Quality of Life Bronchiectasis
SAE	Serious Adverse Event
SPC	Summary of Product Characteristics (in Dutch: officiële productinformatie IB1-tekst)
SUSAR	Suspected unexpected serious adverse reaction
TIS	Tobramycin Inhalation Solution
WMO	Medical Research Involving Human Subjects Act (in Dutch: Wet Medisch-wetenschappelijk Onderzoek met Mensen)

## SUMMARY

**Rationale:** Patients with bronchiectasis often have exacerbations of their disease. These exacerbations influence the quality of life. In patients with cystic fibrosis (CF) longterm inhaled antibiotics lower the bacterial load in bronchial secretions and have positive effect on the number of exacerbations, lung function and quality of life (QoL). In patients with non-CF bronchiectasis colonized with *Pseudomonas aeruginosa* studies with tobramycin inhalation solution (TIS) are limited, however with only five trials to date. In present study the value of maintenance TIS will be investigated in patients with non-CF bronchiectasis colonized by different bacterial species sensitive for tobramycin.

**Objective:** The primary outcome of the study is a 50% reduction in exacerbation rate in patients using maintenance TIS (OD). Secondary outcome parameters are lung function (FEV1, FVC), QoL (QOL-B), LTRI-VAS, Leicester cough score, bacterial load in sputum and tobramycin resistant pathogens.

**Study design:** A randomised, double blind placebo controlled, multicenter study.

**Study population:** Patients aged  $\geq 18$ -year-old with confirmed bronchiectasis by (HR)CT and at least two exacerbations during previous 12 months.

**Intervention (if applicable):** During the study each group (placebo, intervention) receives TIS or placebo, once daily 300mg/5ml for at least 9 months and up to 12 months.

**Main study parameters/endpoints:** The primary endpoint is a reduction of exacerbations that patients suffer during the treatment period. Next to this parameter we expect to show a significant beneficial effect on lung function parameters, QoL, bacterial load of pathogens in sputum and tobramycin resistance.

**Nature and extent of the burden and risks associated with participation, benefit and group relatedness:** After informed consent patients have 3 monthly visits. During the visits patients have to deliver a sputum sample, fill in the QoL questionnaires and a spirometry will be performed according the study schedule. Also a blood sample will be taken during the visits. All patients are instructed to use the nebulizer adequately. The whole procedure of TIS (preparation, inhalation and cleaning) takes approximately 15 minutes. Adverse effects consist of cough, wheezing and dyspnoea. In general practice salbutamol is used before nebulizing TIS, to relieve these symptoms. TIS has already been used by a number of patients with bronchiectasis and is well tolerated. Safety of TIS will be assessed during each contact.

## 1. INTRODUCTION AND RATIONALE

Non-cystic fibrosis (non-CF) bronchiectasis is a chronic disorder of the major airways characterized by permanent dilation and destruction. The origin of bronchiectasis varies, but the presence of microbial infection and a persistent inflammatory response are characteristic for the disease. Colonization of the airway by bacteria stimulates an inflammatory response, which can become chronic if the infection is not eradicated. Chronic inflammation causes host-mediated lung damage leading to a vicious cycle of events and decline in lung function. This vicious cycle of infection and inflammation periodically develops into pulmonary exacerbations that are characterized by the following symptoms: changes in sputum production and purulence, increased dyspnoea, cough, wheezing, fever and fatigue. These exacerbations maybe associated with changes in chest sounds, radiographic abnormalities, but also lead to a decreased exercise tolerance and spirometer values. Bacteria isolated from the sputum of patients with bronchiectasis include *Streptococcus pneumoniae*, *Staphylococcus aureus*, *Haemophilus influenzae*, and other gram-negative bacteria including *Pseudomonas aeruginosa*. *P. aeruginosa* may appear later in the disease and causes more extensive and severe symptoms than the other bacteria. Non-CF bronchiectasis patients with *P. aeruginosa* infection have more hospitalizations, a worse quality of life (QoL), and a more rapid decline in lung function than patients with other lung infections. For other Gram-negative bacteria the progression of bronchiectasis as disease is less well known. Treatment of patients with non-CF bronchiectasis consists of postural physiotherapy, therapy with bronchodilators if reversible airflow obstruction is present, sometimes inhaled corticosteroids as a local anti-inflammatory agent, and antimicrobial therapy including immunomodulating therapy. Treatment of recurrent respiratory infections is the cornerstone in patients with chronic suppurative lung disease. It has been reported that long-term systemic antibiotic treatment results in significant improvements in respiratory symptoms, pulmonary exacerbations, and health-related QoL in patients with severe bronchiectasis. However, systemic antibiotics frequently fail to eradicate lung infections despite intensive therapy. In addition, relapse may occur when the antibiotics are stopped, and resistance frequently occurs with long-term use of systemic antibiotics. An attractive alternative is the use of an inhaled antibiotic that delivers drug in high concentrations directly to the site of infection, eliminating the need for high systemic concentrations and reducing the risk of systemic toxicity or gastrointestinal side effects. Tobramycin inhalation solution (TIS) has been introduced for the long-term management of chronic *P. aeruginosa* infection, with a Cochrane review suggesting some benefit from TIS in terms of lung function and pulmonary exacerbation rate but also concern regarding an increase in antibiotic resistance. The rationale for intermittent administration of tobramycin was based on the observation that during the treatment-free period tobramycin sensitive pathogens may repopulate the lower airways. A recent registry study examining data from the Cystic Fibrosis Foundation's Patient Registry has suggested that TIS use is associated with reduced mortality. TIS has also been demonstrated to be effective in delaying re-infection in those with early *P. aeruginosa* infection. Because secretions in the non-CF bronchiectatic airways are similar to the purulent mucus found in the CF airways, and because pulmonary complications and progression of disease in non-CF bronchiectasis is similar to CF bronchiectasis, many centers treat patients with bronchiectasis using aerosolized TIS. There have been only a few small studies of aerosolized antibiotics to treat

pseudomonas infection in subjects with non-CF bronchiectasis. The study of Drobnic showed that TIS has effect on the rate of hospitalization and bacterial density of sputum. However, pulmonary function and QoL were not influenced. In another study symptoms and QoL were improved. Furthermore, the risk of adverse events such as bronchospasm may be more common in adults with non-CF bronchiectasis than reported in the CF population. No data is available of the effect of maintenance use of TIS in non-CF bronchiectasis colonized by *non Pseudomonas aeruginosa* Gram negative bacteria.

It is known that the antibiotic pharmacokinetics of CF-bronchiectasis differs from non-CF bronchiectasis. The twice-daily TIS dosing regimen in CF is based in large part on studies of tobramycin concentrations in expectorated sputum after administration of a single dose to adolescents and adults with CF. No data are available of the sputum half-life of TIS in non-CF bronchiectasis. Most of these studies used the 4 weeks on-off protocol. In this study we intend to establish the efficacy of once daily dosing of tobramycin. This is supported by knowledge that its bactericidal activity is concentration-dependent with a long post-exposure antibiotic effect. Studies of intravenous administration of tobramycin and other aminoglycosides have shown that once daily dosing is equivalent in terms of antimicrobial efficacy compared to more frequent dosing. Therefore a strong body of evidence supports once daily administration of tobramycin.

The present study has been designed to answer the question whether maintenance treatment with TIS once daily may reduce the number of exacerbations in non-CF bronchiectasis compared to placebo. As written above, the previous studies in patients with non-CF bronchiectasis are limited, small and open label. Next to this argument, it is unknown if extrapolation of the data collected in patients with CF bronchiectasis is justified. That is the reason why the British and Dutch guideline research recommendation mention that randomised controlled trials are needed to investigate the efficacy of nebulised antibiotics in patients with bronchiectasis chronically colonised with *P. aeruginosa* and other organisms. This study is designed as a randomized controlled trial, and TIS will be compared to placebo.

## 2. OBJECTIVES

### Primary Objective:

The primary objective of the study is to determine whether maintenance use of TIS once daily (OD) as compared to placebo may reduce the number of exacerbations per year in patients with non-CF bronchiectasis.

### Secondary Objective:

The secondary objective of this study is to evaluate the effect of TIS treatment on time to next exacerbation, airflow limitation (FVC% predicted, FEV1% predicted), LRTI-VAS, Quality of Life-Bronchiectasis (QOL-B), Leicester cough score, bacterial load in sputum and tobramycin resistance, including MIC values, depending on the capabilities of the microbiological laboratory.

### 3. STUDY DESIGN

This study will be set up as a randomized, placebo controlled, multicenter study to evaluate the efficacy and safety of Tobramycin Inhalation Solution (TIS) compared to placebo. The target group are patients with non-CF bronchiectasis with recurrent exacerbations ( $\geq 2$  per year) and colonized by Gram-negative bacteria (including *Haemophilus influenzae*) and/or *Staphylococcus aureus* in sputum. A sufficient number of subjects across 6 sites will be enrolled to ensure 58 patients. These patients are randomized in a 1:1 ratio of TIS OD (29 patients) to placebo OD (29 patients). The study will compare the number of exacerbations for 52 weeks, as well as the other secondary endpoints.

During the study patients visit the outpatient ward. During these visits' actual medical history, physical examination and questionnaires are obtained. Next to these sputum examination, spirometry and safety tests (lab examination, diary card) are performed. Study medication starts after the run-in period.

This study will consist of an up to 30-day screening phase, a treatment phase of 52 weeks, and a washout phase of 4 weeks.

Participating patients are randomized to one of the two study arms and will be treated for at least 9 months and up to 12 months in a double-blind fashion with placebo or TIS 300mg OD. Sputum samples will be collected from each subject for culture. At the Screening Visit (Visit 0) subjects will review and sign the informed consent form (ICF) and the screening procedures will be completed. Subjects meeting all study eligibility criteria will be randomized 1:1 to receive once daily inhaled treatment with either TIS OD or placebo. Subjects will have a screening visit and 6 additional scheduled visits during the study. Subjects will receive their first dose of study drug at the study site on day 1 during visit 1, and on day 7 they will be contacted by phone for the assessment of compliance and tolerance with study drug. Further visits are scheduled with 12-week intervals. Visit 7, which is the final visit of the study, will be conducted 4 weeks after the end of treatment period (see figure 1). At visit 1, subjects will be instructed on daily study drug administration by self-administering study drug under the supervision of study personnel at the site; subjects will self-administer study drug during the complete study period.

[figure not shown]
Efficacy parameters will include assessment of pulmonary exacerbations, spirometry, LTRI-VAS, QOL-B and Leicester cough questionnaires. Microbiological response measurements will include semi-quantitative density of pathogens in sputum, including the tobramycin minimum inhibitory concentration (MIC) for isolated pathogens. Safety parameters will include assessment of AEs, serial spirometry findings, clinical laboratory test results, vital signs measurements, physical examination. Study drug is dispensed on the regular visits. The first patients will be enrolled in the summer of 2016, with a treatment period of 12 months, we expect to terminate the study 31-01-2020.

In subjects who experience a pulmonary exacerbation, every effort should be made to continue their allocated inhaled study drug, unless the study drug is not tolerated, or the pulmonary exacerbation is believed to be related to study drug. All subjects who receive any study drug need to complete the visit 7 assessments. Subjects who are prematurely withdrawn from study drug will be encouraged to

remain in the study and attend subsequent study visits; at a minimum, they should complete the visit 7 assessments as an early termination visit.

An independent expert will be established to conduct periodic reviews of subject safety for this protocol. The independent expert will also perform a blinded analysis of the pulmonary exacerbation data to check whether the assumptions for sample size estimation are valid, and if they are not, the sample size may be increased.

This study will be conducted in the Noordwest Ziekenhuisgroep, Canisius ZH Nijmegen, Spaarne Gasthuis Hoofddorp, Zuyderland MC Heerlen, VU Medical Center Amsterdam and UMC Utrecht.

## 4. STUDY POPULATION

### 4.1 Population (base)

Non-cystic fibrosis bronchiectasis remains an important cause of chronic respiratory morbidity with a considerable healthcare. The prevalence and incidence of bronchiectasis are not known accurately, however in the last years, there is an increase in prevalence. In this study a total of 58 patients with clinically significant and radiological proven bronchiectasis are recruited from the outpatient clinic. Patients have at least two pulmonary exacerbations in the past year, for further inclusion and exclusion criteria see 4.2 and 4.3. The patients will be enrolled in the study and will be divided into two equally groups of 29 patients.

### 4.2 Inclusion criteria

In order to be eligible to participate in this study, a subject must meet all of the following criteria:

1. Age  $\geq$  18 years
2. The presence of chronic respiratory symptoms such as cough, dyspnoea, expectoration of sputum
3. Confirmed non-CF bronchiectasis by (HR)CT
4. Documented history of at least 2 pulmonary exacerbations treated with courses of antibiotics within 12 months before inclusion.
5. No course of antibiotics or maintenance antibiotics (except for macrolides) 1 month prior to the start of the study.
6. Minimal one documented sputum or BAL-fluid culture with gram-negative bacteria or *S. aureus* within 12 months.
7. Growth of protocol defined pathogens in sputum

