### 4.3 Exclusion criteria

A potential subject who meets any of the following criteria will be excluded from participation in this study:

1. Any exacerbation within the month prior to the start of the study
2. Diagnosis of cystic fibrosis
3. Active allergic bronchopulmonary aspergillosis (ABPA)
4. Any oral, IV or inhaled antibiotics (except for macrolides) within 1 month prior to the start of the study
5. Any IV or IM corticosteroids or change in oral corticosteroids ( $>$  10 mg) within 1 month prior to the start of the study
6. Any change/start treatment regimens macrolides, hypertonic saline, inhaled mannitol or other mucolytics, corticosteroids within 1 month prior to the start of the study
7. Severe immunosuppression or active malignancy
8. Active tuberculosis
9. Chronic renal insufficiency (eGFR  $<$  30 ml/min)
10. Use of loopdiuretics, urea or mannitol
11. Earlier diagnosed hearing impairment, balance disorders or neuromuscular disorders

12. Serious active haemoptysis
13. Have received an investigational drug or device within 1 month prior to the start of the study
14. Serious or active medical or psychiatric illness
15. Pregnancy and child bearing
16. History of poor cooperation or non-compliance
17. Unable to use nebulizers
18. Allergic for tobramycin or NaCl 0.9%

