#### **4.4 Sample size calculation**

The hypothesis is that prolonged treatment with tobramycin reduces the number of exacerbations per patient by 50%. This reduction seems clinically relevant and is based on the assumption that maintenance treatment with TIS OD as well as intermittent TIS BID is comparable to that of azithromycin treatment. This assumption is derived from the data of the BAT trial (placebo: mean 2,1 exacerbations (sd 1.6); azithromycin: mean 0,8 exacerbations (sd 1.1). The reduction in percentage is used for the determination of trial size.

We used a poisson regression model to determine group size. For type I error and type II error 0.05 and 0.2 were used respectively. The hypothesis will be tested two sided. With a baseline exacerbation rate of 2.1 in the placebo group and an expected response rate ratio of 0.5 with an exposure time of 1 year a total of 18 evaluable patients are required to be on each treatment arm.

With a drop-out percentage of 30% we must include totally 48 (24 patients per group) patients.

Due to unforeseen reasons we initially include two extra patients per group. But after the interim analysis three extra patients will be included in the study, because the drop-off percentage is higher as expected in advance. Reason for discontinuation of the study is the intensive treatment and cleaning schedule of the inhaled study medication. So, with a total of 58 patients (29 per group) with bronchiectasis, and not the initially 52 patients (26 per group), we expect to achieve the intended effect size.

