### 5.2 Use of co-intervention

All co-medications are allowed, except for any oral (except for macrolides), IV or inhaled antibiotics within 1 month prior to the start of the study and any IV or IM corticosteroids or change in oral corticosteroids (> 10 mg) within 1 month prior to the start of the study. Immunosuppressive agents such as azathioprine, chemotherapeutic agents, and TNF $\alpha$  inhibitors are prohibited. Also, any change/start treatment regimens of macrolides, hypertonic saline, inhaled mannitol or other mucolytics, within 1 month prior to the start of the study are prohibited. Also, the use of loopdiuretics, mannitol or urea are prohibited.

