## **7.3 Study procedures**

Patients with bronchiectasis and who fulfil the inclusion and exclusion criteria will be asked to participate in the study. After a run-in period of 4 weeks' patients will be randomized to receive one of the two possible treatment regimens: TIS OD 300 mg daily or placebo. Administration will be continuous for the full 12 months. According to the parallel group design patients will be treated for 52 weeks. After completing the intervention period patients will have a follow-up (wash out period) of 4 weeks. This wash-out period was considered to be one month, in which time the antimicrobial effect of the antibiotic supposedly disappears, as suggested in earlier studies.

Subjects will be evaluated at run-in = visit 0 (week -4), visit 1 (day 1- start of the study), visit 2 (week 13), visit 3 (week 26), visit 4 (week 39), visit 5 (week 52: end of treatment) and visit 6 (run-out; week 56: end of the study). One week after start of treatment a phone call will be scheduled. Clinical, laboratory, and bacteriology evaluations will be determined according to the schedule (Figure 1: study schedule). Subjects who terminate treatment should be followed for the same period as those who complete the study, according to the study schedule.

During the study any changes in medical condition and compliance with medication will be filed in the diary card.

At visit 1, after randomisation, a tolerance test with either TIS or placebo (blinded according to randomisation) will be performed. Before nebulizing TIS patients are treated with salbutamol 200mcg using an AeroChamber. During tidal breathing patients inhale 300mg TIS or placebo (at room temperature) by using the Innospire Deluxe nebulizer with mouthpiece during approximately 5 minutes. If patients develop a moderate-severe bronchial obstruction, patients are excluded from the study. The severity of bronchial obstruction and coughing is assessed by a specialized nurse, the respiratory physician or the own GP. An exacerbation is defined as the presence of three or more of the following symptoms or signs for at least 24 hours: increased cough, increased sputum volume, increased sputum purulence, haemoptysis, increased dyspnoea, increased wheezing, fever (>38.5°C)

or malaise, and the treating physician agreed that antibiotic and/or prednisolone therapy was required.

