#### **9.4.3 Primary study parameter(s)**

A poisson regression model was used to analyse the primary outcome measure, evaluating both events and exposure (person-time), employing a quasilikelihood factor (with overdispersion correction), and incorporating the following covariables: treatment assignment, age, sex, smoking history, and presence of *P aeruginosa* and azithromycin maintenance use at baseline.

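### Any maintenance macrolide is allowed at entry, but the primary model adjusts only for azithromycin, so users of another macrolide are coded as non-users (minor)

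*Combined protocol and SAP*

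**What the plan says.** Eligibility refers to macrolides as a class and names no agent:

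- Section 4.2, item 5: "No course of antibiotics or maintenance antibiotics (except for macrolides) 1 month prior to the start of the study".
- Section 4.3, item 4: "Any oral, IV or inhaled antibiotics (except for macrolides) within 1 month prior to the start of the study".
- Section 4.3, item 6 excludes "Any change/start treatment regimens macrolides, hypertonic saline, inhaled mannitol or other mucolytics, corticosteroids within 1 month prior to the start of the study", and section 5.2 repeats the one-month window for macrolides. Section 7.3 places the start of the study at "visit 1 (day 1- start of the study").

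The analysis is narrower. Section 9.4.3 fits a Poisson regression with an over-dispersion correction. Its only macrolide term is "azithromycin maintenance use at baseline". Section 7.1.3 likewise lists azithromycin maintenance only.

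Sections 7.2 and 9.2 describe 1:1 randomisation and name no stratification factor. Concomitant medication is recorded at visits 0 and 1 (section 7.3).

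Two further passages bear on the secondary observation. Section 4.2, item 4 requires "Documented history of at least 2 pulmonary exacerbations treated with courses of antibiotics within 12 months before inclusion". Section 4.4 takes its planning figures from the cited azithromycin trial: "placebo: mean 2,1 exacerbations (sd 1.6); azithromycin: mean 0,8 exacerbations (sd 1.1"). The control rate is set at the placebo value, 2.1 per year.

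**The concern.** The covariate is there to separate patients whose exacerbation rate is already lowered by a macrolide from those whose rate is not. As worded, it does so for one agent while entry is open to the whole class. A patient on a different maintenance macrolide satisfies every criterion and then enters the model as unexposed. The non-user stratum becomes a mixture of two expected rates, and the model cannot tell them apart.

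Two things are at stake. The unexplained spread within that stratum adds to over-dispersion, which costs precision. And with 29 patients per arm and no stratification named, this covariate is the only stated correction for a chance imbalance in macrolide use. It cannot correct an imbalance in users whom it does not identify.

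A lesser matter sits beside this. The exacerbation history looks back 12 months and the macrolide rule only one. A patient may therefore qualify on exacerbations that preceded the macrolide.

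**Working it through.** **1. The plan's own figure.** Inputs from 4.4 and 9.1: two-sided alpha 0.05, power 0.80, placebo rate 2.1 per year, rate ratio 0.5, exposure 1 year, phi = 1, equal groups. The cited Poisson-regression formula is

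N = phi × (1.960 × √V0 + 0.8416 × √V1)² / (rate × (ln RR)²), with V0 = 4 and V1 = 1/0.5 + 1/(0.5 × 0.5) = 6.

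This gives 35.46, rounded up to 36, as stated. Power at 36 is 0.805.

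**2. Does the coding gap bias the rate ratio?** Let a share q of the coded non-users take another macrolide. Assume that they exacerbate at 0.8 per year without tobramycin, that the rest do so at 2.1, and that tobramycin halves both rates. The placebo rate is 2.1(1 − q) + 0.8q and the tobramycin rate is exactly half of it. The ratio stays at 0.5 for every q, so with randomised groups there is no systematic bias.

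**3. Extra variation.** In the placebo arm, phi = 1 + q(1 − q)(2.1 − 0.8)² / rate. In the tobramycin arm both rates are halved, so the excess over 1 is halved too.

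| q (assumed) | Placebo rate | phi, placebo | phi, tobramycin |
|---|---|---|---|
| 5% | 2.035 | 1.04 | 1.02 |
| 10% | 1.97 | 1.08 | 1.04 |
| 20% | 1.84 | 1.15 | 1.07 |

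Example for 20%: 0.2 × 0.8 × 1.69 / 1.84 = 0.147. In the variance of the log rate ratio the arms weigh 1:2, because the tobramycin arm has half the events. The combined inflation is therefore (1.04 + 2 × 1.02)/3 = 1.03 at 5% and (1.15 + 2 × 1.07)/3 = 1.10 at 20%.

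**4. Chance imbalance, as an illustration.** Suppose three users of another macrolide fall in one arm of 29 and none in the other, with no azithromycin users. Before any treatment effect, the first arm's expected rate relative to the second is (26 × 2.1 + 3 × 0.8)/(29 × 2.1) = 57.0/60.9 = 0.94. The covariate as worded would leave this 6% shift uncorrected.

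**5. Secondary observation: recent starters.** Let a share m of patients have qualified before starting a macrolide. Assume that they exacerbate at 0.8 per year and the rest at 2.1, with phi = 1. The 58 randomised, less 30% drop-out, leave about 40 evaluable (58 × 0.7 = 40.6).

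| m (assumed) | Control rate | N for 80% power | Power at 36 | Power at 40 |
|---|---|---|---|---|
| 0 | 2.10 | 36 | 0.805 | 0.84 |
| 10% | 1.97 | 38 | 0.78 | 0.82 |
| 20% | 1.84 | 41 | 0.76 | 0.80 |
| 30% | 1.71 | 44 | 0.73 | 0.77 |

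**The case against.** The best defence of the wording is that azithromycin is the only macrolide antibiotic the documents name, and that 7.1.3 and 9.4.3 agree with each other. If every macrolide user in the trial takes azithromycin, nothing is miscoded. The over-dispersion correction also keeps the standard error honest when some heterogeneity is left over. Both points stand, and they are why the matter is minor. They do not remove the mismatch: the entry criteria admit other agents, and the over-dispersion correction widens the interval without recovering the lost precision or correcting an imbalance.

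A reader might infer something stronger from the 12-month and one-month windows: that recent starters undermine the comparison, and that the qualifying exacerbations should have to occur on the current macrolide regimen. The documents do not support this.

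- Recent starters are randomised like everyone else. Their presence can lower the event rate but does not bias the comparison.
- They are not uninformative. At 0.8/2.1, each contributes about 38% of a non-user's expected events.
- Their share is not given. The 0.8 is another trial's azithromycin-arm mean, so it is only an assumption for patients selected by this trial's criteria.
- The plan already has means to detect a low event rate. Section 3 provides a blinded check of the sample size assumptions with a possible increase, and 9.4.6 repeats the power calculation at the interim.
- With about 40 evaluable, power is still near 0.80 at a 20% share. That margin is uncertain, because 4.4 says drop-out is higher than expected. Against that, the analysis is by intention to treat with person-time, so drop-outs still contribute exposure.
- Such a rule would narrow the population to patients who exacerbate despite a macrolide and could delay a recent starter by up to a year. The sample size text already reports a change following the interim, so the rule would reach only the remaining recruits.

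**Conclusion.** The mismatch between the entry criteria and the primary model is real. As written, an eligible user of a maintenance macrolide other than azithromycin is analysed as a non-user. The consequence is some loss of precision and an incomplete correction of chance imbalance, with no systematic bias in the rate ratio.

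It is probably small. If 5% to 20% of the non-user stratum were miscoded, phi from this source would be about 1.04 to 1.15 in the placebo arm, and the variance of the log rate ratio would rise by about 3% to 10%. These figures assume rates of 0.8 and 2.1 per year and a common rate ratio of 0.5. The miscoded share is not in the documents and could be zero.

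The entry of recent macrolide starters is a secondary observation about a planning assumption. It is not a design fault that calls for different eligibility. Priority: minor.

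**What to change.** In 9.4.3, replace the azithromycin term with maintenance macrolide use at baseline (any macrolide, yes or no), derived from the concomitant medication recorded at visits 0 and 1. Make the change before unblinding, and bring 7.1.3 into line. The cost is one phrase in each section and no new data.

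Optionally, state in 4.4 that the control rate of 2.1 is a placebo-arm rate and that macrolide users, including recent starters, are eligible. Where the macrolide start date was recorded, examine duration of use in a sensitivity analysis. Section 7.3 does not explicitly ask for that date, so this may be possible for only some patients. No change to the eligibility criteria is needed.
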